An article has been published in *British Journal of Nursing* (2) about the consensus guidelines to encourage nurses to choose ostomy products based on assessment of the individual body profile of the user. The paper shows how the consensus guidelines were developed and presents concept and purpose of the 6 steps in the Body Assessment Tool in hope of providing nurses a more structured and "right from the start" approach when choosing ostomy products. However, the Body Assessment Tool needs to be evaluated in clinical settings to document the usability among nurses and to explore its impact on selection of ostomy product(s) together with a potential improvement of leakage incidences and the user's leakage-related quality of life using the validated OLI score (Ostomy Leakage Impact Tool)(3).

Furthermore, it is of interest to explore usability of The Body Assessment Tool in the group of newly stoma patients (i.e. newly patient discharged (NPD)) as they may have a potentially larger extent of change of their peristomal body profile post-surgery compared to experienced people with a stoma (i.e. veterans). A subgroup of NPDs will therefore be recruited at one clinical site,
Meilahden tornisairaala, Finland

2. Hypothesis

The hypothesis is that with the Body Assessment Tool in combination with the use of the current guidelines and practices, nurses will be able in a standardised way to choose the most appropriate ostomy product(s) for the given user and may thereby help improving the QoL of the user by reducing the users concerns about leakage and preventing the incidences of leakage.

3. Objectives

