Prior to screening the nurse identifies potential patients who require a re-evaluation of their current ostomy products due to ongoing product issues (please refer to section 5 '*In- and exclusion criteria*'). If the patient is interested in study participation the subject must sign an informed consent after having received verbally and written information about the study. When signed the subject can undergo the screening assessment and if found eligible the subject can be enrolled in the study.

Following enrollment, the nurse will perform body profile assessment (the stoma and peristomal area) of the subject using the Body Assessment Tool. Based on the result the nurse will select the most appropriate ostomy product(s) for the subject. The body assessment tool that has been filled out for each participant will be stored in the study participant file. At the visit the subject will also be asked to evaluate the impact of leakage and fear of leakage on their QoL using the OLI-score together with recalling the number of leakage incidences the last 7 days. This questionnaire will also be stored in the study participation file. The participant

will leave the clinic with new ostomy products and be instructed to use them for the next 4-5 weeks. The participant will also receive a second questionnaire to be filled in at home after 4-5 weeks.

After 4-5 weeks, the nurse will contact the subject by phone or in a new scheduled visit to the clinic to remind the participant, if needed, to evaluate the impact of leakage on QoL/fear of leakage using the OLI score together with recalling the number of leakage incidences in the last 7 days. The subjects will send the questionnaires with a patient code directly to Coloplast. Patients will be encouraged to send in the second questionnaire even if they have discontinued using the recommended ostomy products also to know the reason for discontinuation.

After all subjects at a given study site have been included, the nurse will evaluate the Body Assessment Tool based on his/her experience of the tool in the clinic, using the Nurse Evaluation Form.

Anonymous data – including the questionnaire and the body assessment tool for each participant and the Nurse Evaluation Form will be sent to Coloplast for analysis.

5. Inclusion- and exclusion criteria

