5.3. Exclusion criteria for veterans and NPDs

The subject will not be eligible for enrollment if the subject:

- Requires a caretaker to change ostomy product(s) on the user
- Is pregnant (mainly due to substantial change of body profile during intervention)
- Is lactating (mainly due to potential weight loss and substantial change of body profile during the intervention)
- Does not have the resources personally, mentally, or physically to participate in the intervention (judged by the ostomy nurse)
- Changes his/her ostomy products (bag or plate) during the intervention period (withdraw of data)

6. Number of patients with rationale for choice

A minimum of 160 subjects will be enrolled in the study. At least 40 individuals with a stoma will be enrolled from each Nordic country (i.e. Denmark, Sweden, Norway and Finland). The subjects will be recruited from at least 3 clinics in each country and each clinic will recruit at least 5 participants to the study. The total number of participants is based on what seems feasible to enroll. As the primary endpoint will be presented using descriptive methods there is no requirements on the sample size.

The OLI score results are not the primary outcome of the study and the >160 numbers of subjects are sufficient.

7. Statistical considerations

Data from the Nurse Evaluation Form will be presented using descriptive methods.

The OLI score will be presented using both descriptive methods (i.e. sub-questions) and quantitative methods (i.e. the 3 domain scores: 'emotional impact', 'usual and social activities' and 'coping and in control').

Change of the domain scores 'emotional impact', 'usual and social activities' and 'coping and in control' and number of leakages pre-and post-transition of ostomy products will be analyzed by using paired t-test. All three domain scores are designed to range from 0-100. Higher scores represent better levels of functioning. The domain scores will be calculated as mean of the responses to each question or item within a domain (the method to estimate the domain scores is described in Appendix C).

The number of leakage episodes/7 days) will be analysed by quantitative methods (paired t-test).

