The exploratory NPD data from the clinical site Meilahden tornisairaala, Finland will not be pooled with the veteran data as the two groups can be potentially very different in the change of peristomal body profiles during the study period. This makes the two groups less comparable and the NPD data will therefore be analysed separately.

There will be no comparison to other types of products or body assessment tools. In case subjects change to other ostomy products during the intervention period the data of the given subject will not be included in the final data of the study.

8. Primary and secondary outcomes

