		I navelhöjd	Stomin är placerad i navelhöjd.
		Under navelhöjd	Stomin är placerad under navelhöjd.

6	Stomimynningens placering i förhållande till huden	Över hudplanet	Stomimynningen är över hudplanet.
		I nivå med hudplanet	Stomimynningen är i nivå med hudplanet.
		Under hudplanet	Stomimynningen är under hudplanet.

Konsistensen på det som kommer ut från stomin

Konsistans:	Tjock avförling	
	Lös avförling	
	Urin	

Val av produkt

Typ av häfta	Typ av system	Typ av påse
Platt	1-delssystem	Tömbar påse
Convex Soft	2-delssystem (klick/mekanisk koppling)	Sluton påse
Convex Light	2-delssystem (haftkoppling)	Urostomipåse
Convex Deep		
Konkav		
Annat		

Tillbehörsprodukter

Övriga faktorer som har haft betydelse vid val av produkt (markera gärna med flera kryss)

Den peristomala huden	Patientens tillgång till hjälp i hemmet
Patientens allmänna tillstånd	Patientens förmågor

©Coloplast AB, Coloplast Care / Ostomy Care / Wound & Skin Care / Interventional Urology

Coloplast AB, [name], Sweden.
www.coloplast.se Coloplast är ett registered varumärke, dit är Coloplast AB. © 2020-08. Alla rättigheter tillvarat Coloplast AB.

13. Appendix B - Nurse Evaluation Tool

Utvärdering

Nordisk Konsensus Studie

Sjukhus: _____

Avdelning: _____

Stomiterapeut: _____

Datum: _____

1	Hur många stomiopererade har deltagit i studien? _____					
2	Hur väl upplever du att verktyget Kroppsprofil fungerar i klinisk praxis (där 6 är bäst). Markera med x					
	1 	2 	3 	4 	5 	6 
3	Hur väl upplever du att det fungerar att utgå ifrån patientens kroppsprofil, när du ska välja stomiprodkuter? (där 6 är bäst). Markera med x					
	1 	2 	3 	4 	5 	6 
4	Upplever du att verktyget Kroppsprofil hjälper till att lyfta kvaliteten på behandlingen? (där 6 är bäst). Markera med x					
	1 	2 	3 	4 	5 	6 

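### Does section 6 need a newly-discharged-patient (NPD) number, a counting rule and a nurse-form count before it can call 160 subjects sufficient?

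*Combined protocol and SAP*

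**What the plan says.** Section 6 (Number of patients with rationale for choice) states "A minimum of 160 subjects will be enrolled in the study" and "At least 40 individuals with a stoma will be enrolled from each Nordic country". It asks for at least 3 clinics per country and at least 5 participants per clinic. The total is openly based on feasibility, and the section says that a descriptive primary endpoint sets no sample-size requirement. On the secondary quality-of-life outcome it says "The OLI score results are not the primary outcome of the study and the >160 numbers of subjects are sufficient".

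NPDs appear elsewhere. The introduction says that "it is of interest to explore usability of The Body Assessment Tool in the group of newly stoma patients" and that "A subgroup of NPDs will therefore be recruited at one clinical site". Section 4 has them follow the veterans' protocol and treats their data as exploratory. Section 7 says that their data "will not be pooled with the veteran data as the two groups can be potentially very different".

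The primary outcome (section 8.1) is the nurse's rating of the tool on 6-point items. Section 4 fixes the timing: "After all subjects at a given study site have been included, the nurse will evaluate the Body Assessment Tool". Section 4 also gives 20 to 40 sites. Appendix B opens with fields for hospital, department and stoma therapist, and its item 1 ("Hur många stomiopererade har deltagit i studien") asks for a single count of participants, not split into NPDs and veterans.

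**The concern.** Three numbers that a reader expects beside a sufficiency statement are absent.

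- **NPDs.** There is no target, and no rule on whether they count toward the 160 or Finland's 40. Because they are analysed separately, each NPD counted inside the 40 is one veteran fewer at the floor. Two people monitoring recruitment could close Finland at different veteran numbers, and the separate NPD paired tests could be run on very few pairs.
- **Nurse forms.** The unit of the primary outcome is the form, not the patient, so 160 subjects says nothing about how many usability ratings there will be.
- **NPD usability.** With one NPD site and one form per site, it would rest on a single form. If that site also enrolled veterans, the form would mix the two groups.

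At stake would be the precision of the veteran analyses, the denominator of the primary outcome, and whether NPD usability can be described at all.

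**Working it through.** **1. The plan's own figure.** 4 countries × 40 = 160, which reproduces the stated minimum. The clinic floors alone give 4 × 3 = 12 clinics and 12 × 5 = 60 subjects, so the country floors set the total. The documents give no SD, effect size, alpha or power, so there is no power calculation to reproduce.

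**2. How far the counting rule can move the veteran number.** Assume that NPDs count, Finland stops at exactly 40, the other Finnish clinics supply at least 5 each, and the NPD site recruits only NPDs.

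- Most NPDs with 3 Finnish clinics (section 6 minimum): 40 − 2 × 5 = 30. Veterans: 160 − 30 = 130.
- Most NPDs with 5 Finnish clinics (20 sites split evenly, assumed): 40 − 4 × 5 = 20. Veterans: 160 − 20 = 140.
- Fewest NPDs (clinic floor): 5. Veterans: 160 − 5 = 155.

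**3. What that does to precision.** The 95% half-width of a mean paired change, in SD of the change, is t(0.975, n − 1)/√n. The detectable effect is for a two-sided 5% paired t-test with 80% power (my assumptions).

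| Veteran pairs | Half-width (SD) | Detectable effect (SD) |
|---|---|---|
| 160 | 0.156 | 0.223 |
| 155 | 0.159 | 0.226 |
| 140 | 0.167 | 0.238 |
| 130 | 0.174 | 0.248 |

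The worst case widens the interval by a factor of about √(160/130) = 1.11. Losses act on both readings alike. At 30% lost or removed (assumed), 160 × 0.7 = 112 pairs give 1.982/√112 = 0.187 SD, and 130 × 0.7 = 91 pairs give 0.208 SD, again a ratio of 1.11.

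**4. The NPD group alone.** Half-widths are 1.24 SD at 5 pairs, 0.72 at 10, 0.47 at 20 and 0.37 at 30. The group may be uninformative if small, and its interval will show that.

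**5. Nurse forms.** At one form per site, section 4 implies 20 to 40, and section 6's clinic floors imply at least 12. With about 80% favourable answers (assumed), exact 95% intervals are 52–98% for 10/12, 56–94% for 16/20 and 64–91% for 32/40. These are wide, but the plan promises only description. At one form per site the NPD site gives 1 form and no estimate of spread.

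**6. Which reading the text favours.** Section 6 counts people with a stoma. The inclusion lists in 5.1 and 5.2 describe veterans and NPDs alike in those terms, and section 4 calls the NPDs a subgroup. The natural reading is that they count. Separate analysis under section 7 does not conflict with that.

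**The case for a change.** The strongest case for a change is that the remedy is cheap and partly time-limited. A few sentences would settle the counting rule, the NPD number and who completes the form. A missing NPD/veteran split in Appendix B cannot be repaired once the form is filled in. Waiving a power calculation for a descriptive endpoint also does not explain how many observations it will have.

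Part of this stands. The plan does not give these numbers, and the word sufficient has no figure behind it. Feasibility is the stated basis, however, and nothing shows the veteran sample to be too small. Without an SD in the documents, a half-width could be quoted only in SD units, not in points on the 0–100 scale.

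The point about the mixed form depends on two things the documents do not say: that the NPD site also enrols veterans, and that it returns only one form. Appendix B identifies the hospital and the individual therapist, so several forms from one site are possible and that site's forms can be picked out. The free-text items 6 and 7 also leave room to describe NPD experience. NPD usability is an interest voiced in the introduction. It is not listed among the objectives in section 3 or the outcomes in section 8.

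**Conclusion.** No change follows. The omissions are gaps that analysts fill sensibly when reporting: the number of NPDs and veterans enrolled and paired, the number of forms received and from which sites, and a label saying that NPD usability comes from one site. The 160 and the 40 are floors, so recruitment may exceed them. Even in the extreme case the veteran half-width moves only from 0.156 to 0.174 SD. That case assumes that NPDs count, Finland stops at exactly 40 with 3 clinics, and 30 NPDs come from one site. The primary endpoint is descriptive, and the NPD data are exploratory and kept apart, so following the plan as written biases no estimate. What remains is a conditional limit on interpretation: if the NPD site enrols both groups and returns one form, its usability rating cannot be attributed to either.

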8.1. Primary outcome

- The usability of the Body Assessment Tool will be based on the Nurse Evaluation Form including the following questions (evaluation performed by the nurse) (6-point scale):
 - How well does the Body Assessment Tool work in a clinical setting?
 - How well does the assessment of the user's body profile work prior to selecting ostomy product(s)?
 - Do you experience that the Body Assessment Tool supports you to increase the quality of the treatment?

8.2. Secondary outcomes

- Rating of the user's leakage associated QoL the last 7 days (i.e. 4-point scale sub-questions) before and after ostomy product change
- Change in domain scoring of fear of leakage and the impact on QoL pre- and post-transition of ostomy product(s):
 - emotional impact
 - usual and social activities
 - coping and in control
- Number of self-reported retrospective incidences of leakage the last 7 days on prior to and after transition to more appropriate ostomy product(s)
- Analysis of connection between body profile, product solution and incidence of leakage

9. Comparison or control group

There will be no comparison to other types of products, body assessment tools or control groups.

Each subject will act as their own control when analysing the difference in the OLI score and number of leakage incidences pre-and post-transition of ostomy product(s).

10. Study follow-up schedule

No follow-up visits or contact with the users are included in the study

11. References

1. Ostomy Life Study 2019, Global Report, Data-on-file, PM-10499

12. Appendix A - Body Assessment Tool

Datum _____

Patient 3000X

Kroppsprofil

[figure not shown]
Utvärdering av den peristomala kroppsformen för att säkerställa det bästa produktvalet

1	Formen på området runt stomtin.	Platt	Området är mer eller mindre i nivå med buken, även om själva huden kan vara glömm.
		Inbuktad	Området sjunker ner i buken och bildar en grop.
		Utbuktad	Området reser sig från buken och bildar en kopp.

2	Den valda ytan kanske inte täcker hela området runt stomin	Helt	Formen täcker hela området runt stomin.
		Delvis	Formen täcker delar av området runt stomin.

3	Är magen mjuk eller fast?	Mjuk	Ytan ger vila för tryck (som motsvarar tryck på en vattenmodell).
		Fast	Ytan motstyrt tryck (som motsvarar tryck under huden).

[figure not shown]
4	Är det ytliga eller djupa veck?	Ytliga	Huden omkring stomin har linjer, dr färd eller rynkig.
		Djupa	Huden omkring stomin har djupa veck av samt rynkor.

5	Stomins placering	Över navelhöjd	Stomin är placerad över navelhöjd.
		I navelhöjd	Stomin är placerad i navelhöjd.
		Under navelhöjd	Stomin är placerad under navelhöjd.

6	Stomimynningens placering i förhållande till huden	Över hudplanet	Stomimynningen är över hudplanet.
		I nivå med hudplanet	Stomimynningen är i nivå med hudplanet.
		Under hudplanet	Stomimynningen är under hudplanet.

Konsistensen på det som kommer ut från stomin

Konsistans:	Tjock avförling	
	Lös avförling	
	Urin	

Val av produkt

Typ av häfta	Typ av system	Typ av påse
Platt	1-delssystem	Tömbar påse
Convex Soft	2-delssystem (klick/mekanisk koppling)	Sluton påse
Convex Light	2-delssystem (haftkoppling)	Urostomipåse
Convex Deep		
Konkav		
Annat		

Tillbehörsprodukter

Övriga faktorer som har haft betydelse vid val av produkt (markera gärna med flera kryss)

Den peristomala huden	Patientens tillgång till hjälp i hemmet
Patientens allmänna tillstånd	Patientens förmågor

©Coloplast AB, Coloplast Care / Ostomy Care / Wound & Skin Care / Interventional Urology

Coloplast AB, [name], Sweden.
www.coloplast.se Coloplast är ett registered varumärke, dit är Coloplast AB. © 2020-08. Alla rättigheter tillvarat Coloplast AB.

13. Appendix B - Nurse Evaluation Tool

Utvärdering

Nordisk Konsensus Studie

Sjukhus: _____

Avdelning: _____

Stomiterapeut: _____

Datum: _____

1	Hur många stomiopererade har deltagit i studien? _____					
2	Hur väl upplever du att verktyget Kroppsprofil fungerar i klinisk praxis (där 6 är bäst). Markera med x					
	1 	2 	3 	4 	5 	6 
3	Hur väl upplever du att det fungerar att utgå ifrån patientens kroppsprofil, när du ska välja stomiprodkuter? (där 6 är bäst). Markera med x					
	1 	2 	3 	4 	5 	6 
4	Upplever du att verktyget Kroppsprofil hjälper till att lyfta kvaliteten på behandlingen? (där 6 är bäst). Markera med x					
	1 	2 	3 	4 	5 	6 

5	
De Internationella Consensus Guidelines rekommenderar att man, utöver att välja produkt baserat på Kroppsprofil, även tar patientens peristomala hud och övergripande situation i beaktning. Genom att överföra det antal gånger de fyra faktoreerna har påverkat valet av produkt från det ifyllda verktyget Kroppsprofil, kan vi bestämma, vilka faktorer utöver Kroppsprofil, som har varit viktigast i valet av produkt.
 
Överför från verktyget Kroppsprofil det antal gånger de fyra faktoreerna har haft påverkan på produktval
			
	Den peristomala huden	Patientens allmänna tillstånd	Patientens tillgång till hjälp i hemmet	Patientens förmågor

Andra förhållanden du har tagit i beaktning:
 <hr/> <hr/>				
6	
Beskriv med egna ord hur du upplever att verktyget Kroppsprofil, som baserar sig på de Internationella Consensus Guidelines, har fungerat i klinisk praxis?
 <hr/> <hr/> <hr/>			
7	
Vill du rekommendera verktyget Kroppsprofil till andra stomiterapeuter/vårdpersonal?
 
Markera med X
			
	JA	NEJ	Varför?	
			<hr/> <hr/>	

Tusen tack för hjälpen!

14. Appendix C – The OLI Score

The below tables show the scoring weights for each item from the OLI score questionnaire.

Domain score 1. Emotional impact

When you thought about your ostomy device and the risk of leakage, what emotions did you feel?

In the last 7 days, due to leakage or worry about leakage...	All of the time	Often	Sometimes	Rarely or never
1. I felt panic	0	1	2	3
2. I felt stressed out	0	1	2	3
3. I felt more afraid about leaks in the future	0	1	2	3
4. I felt worry	0	1	2	3
5. I felt frustrated	0	1	2	3
6. I felt embarrassed	0	1	2	3
7. I felt worried that I might leak	0	1	2	3
8. I couldn't sleep	0	1	2	3
9. I kept waking up at night to check my stoma	0	1	2	3
10. I kept checking my ostomy bag to see if I have leaked	0	1	2	3

Domain score 2. Usual and Social activities

When you thought about your ostomy device and the risk of leakage, how did it affect your activities?

In the last 7 days due to leakage or worry about leakage...	All of the time	Often	Sometimes	Rarely or never	Not applicable
11. I decided to stay at home	0	1	2	3	9
12. I couldn't do light activities	0	1	2	3	9
13. I changed my plans	0	1	2	3	9
14. I was unable to go out and meet family and friends	0	1	2	3	9
15. I avoided close physical contact with family and friends	0	1	2	3	9
16. I did not want to see people	0	1	2	3	9
17. I avoided people	0	1	2	3	9
18. I tried to avoid meeting new people	0	1	2	3	9

Domain score 3. Coping and in control

When you thought about your ostomy device and the risk of leakage, how did it affect your ability to cope?

In the last 7 days, due to leakage or worry about leakage...	All of the time	Often	Sometimes	Rarely or never
19. I felt in control	0	1	2	3
20. I was able to cope	0	1	2	3
21. I felt calm	0	1	2	3
22. I saw my friends as I usually do	0	1	2	3

All three domain scores are designed to range from 0-100. Higher scores represent better levels of functioning. A domain score is estimated as a mean of the responses to each question or item within a domain. This is then divided by the arithmetic difference between the minimum score (0) and the maximum score (3) so that this number then varies between 0 and 1. This is then rescaled between 0 -100. It is important to note that some items in the questionnaire are effectively reversed scored. The need to do this is accommodated by in the scoring algorithm itself rather than in the scoring weights for each question. Scoring formulae for the three domain scores is provided here:

Emotional impact

$$Score = \left(\frac{\sum(Q1, Q2, \dots Q10)}{10} \div 3 \times 100 \right)$$

Usual & social activities

$$Score = \left(\frac{\sum(Q11, Q12, \dots Q18)}{8} \div 3 \times 100 \right)$$

Coping & in control

$$Score = 100 - \left(\frac{\sum(Q19, Q20, \dots Q22)}{4} \div 3 \times 100 \right)$$

Not applicable & Missing data

Where responses are classified as Not applicable then this should be noted in the descriptive summary of the data in any study report. In addition, though for the purposes of scoring the domains these responses should be coded as missing data.

A domain score can be estimated when at least 50% of the items within a domain have been completed. The scale score is estimated in the same way by taking the mean of the items that have been completed. If less than 50% of the items have been completed, then the domain should not be scored for that individual. If there are a high number of participants who fail to complete all the items in the survey, then this should be noted as a limitation in the study report.

References:

- (1) *Creating consensus-based guidelines with 2000 nurses*, Sara James-Reid et al., British Journal of Nursing 2019: <https://www.magonlinelibrary.com/doi/full/10.12968/bjon.2019.28.22.S18>

15. Appendix D – The Leakage Questionnaire

2. Antal läckage och dess storlek

[figure not shown]
Hur många läckage har du haft de senaste 7 dagarna? _____
(se definitionen av läckage nedan)

Vad menar vi med läckage?

[figure not shown]
När du ska bedömma hur många gånger du har haft läckage under de senaste 7 dagarna, vill vi be dig att titta på exemplen nedan. Alla exemplen nedan beskriver läckage. Allt från det lilla läckaget intill stomin; när huden kommit i kontakt med avföring eller urin, till stora läckage där det har läckt ut på kläderna.

Om du under de senaste 7 dagarna kan komma ihåg hur mycket läckage du har haft vid varje läckagetillfälle ber vi dig att även fylla i antal läckage nedan under varje exempel:

[figure not shown]
Läckage - avföring

[figure not shown]
Antal _____

Antal _____

[figure not shown]

Antal _____

Antal _____

Läckage - urin

Antal _____

Antal _____

Antal _____

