3.2. The secondary objectives

- To explore if the use of Body Assessment Tool and related change of ostomy product(s) have an impact on the leakage associated QoL (based on the OLI score)- see appendix C. The OLI score includes three domain scores:
 - emotional impact
 - usual and social activities
 - coping and in control
- To evaluate the incidences of leakage before and after change of ostomy product(s) (the question will be included in a leakage questionnaire in addition to the OLI score – see appendix D).

4. Study design

The study is a 1-sequential, 1-arm, non-randomised, non-blinded, multi-center (between 20 to 40 sites in total) non-interventional 4-5-week clinical investigation in which the Body Assessment Tool will be evaluated for its usability by ostomy nurses using the Nurse Evaluation Form and to explore if the change of ostomy product(s) can reduce the user's concerns about leakage and have a positive impact on QoL related to leakage (estimated by the OLI score). For evaluation of the number of leakage incidences the last 7 days pre- and post-change of ostomy products a questionnaire is prepared including a definition of leakage and images for support.

Blinding is not applicable as change of ostomy product(s) cannot be blinded for either the user or nurse. Randomization is not applicable as there will be no comparison to a specific ostomy product or control group. The subjects will change their ostomy product(s) based on their individual body profile assessment and the selection of ostomy products will vary in between subjects and will not be dictated by this protocol.

The NPD subgroup will follow the same protocol as the veterans. However, the data (NPDs vs. veterans) will not be compared due the potentially difference in the change of peristomal body profile. The NPD data will be regarded and handled as exploratory.

All assessments will be based on questionnaires either completed by the nurse or user. Usability data will only be analyzed using descriptive methods. Whereas the OLI score results will be analyzed by descriptive methods (sub-questions in OLI score) and paired t-test (domain scores). The number of leakage episodes will be analyzed by paired t-test.

The study will include 1 visit at the clinic and at least 1 phone call visit to the user (end-of study phone visit). The number of phone calls will vary depending on the user's need for support.

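### The one-arm before-after tests on OLI and leakage can show change, not effect, and subjects who switch product are dropped although their second questionnaire is requested

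*Combined protocol and SAP*

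**What the plan says.** **Design and analysis.** Section 4 describes one non-randomised arm and states "Blinding is not applicable as change of ostomy product(s) cannot be blinded for either the user or nurse". Section 9 rules out any control group and adds "Each subject will act as their own control when analysing the difference in the OLI score and number of leakage incidences". One 7-day recall at the clinic visit is set against one 7-day recall after 4-5 weeks. Sections 4 and 7 analyse the three OLI domain scores and the leakage count by paired t-test.

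**Aim.** The first objective in 3.2 is "To explore if the use of Body Assessment Tool and related change of ostomy product(s) have an impact on the leakage associated QoL". Section 4 repeats the aim: the product change is to be explored for whether it can reduce concerns about leakage and "have a positive impact on QoL related to leakage (estimated by the OLI score". The second objective in 3.2, on leakage incidences, uses before-and-after wording only.

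**Subjects who switch.** Section 5.3 lists as an exclusion "Changes his/her ostomy products (bag or plate) during the intervention period (withdraw of data", which can be known only after enrolment. Section 7 says "In case subjects change to other ostomy products during the intervention period the data of the given subject will not be included". Section 4 says "Patients will be encouraged to send in the second questionnaire even if they have discontinued using the recommended ostomy products", partly to learn the reason.

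**Forms.** Appendix A, as shown, has one block for the product chosen at the visit. No form, as shown, has a field for the product worn on arrival.

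**The concern.** With one arm, the paired difference contains everything that changed between the two recalls. The documents themselves name or imply several contributors besides the tool and the product:

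- the nurse's re-evaluation under current guidelines and practice (section 2), with support calls: "The number of phone calls will vary" (section 4);
- self-report by subjects who know that their product was changed (section 4);
- change in the peristomal body profile over the study period, expected especially in NPDs (sections 1, 4 and 7);
- removal of subjects who switch product (sections 5.3 and 7);
- regression to the mean, mainly in veterans, who enter because of leakage issues (section 5.1).

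Removal of switchers is the contributor that the plan creates by its own rule, and the one it can largely check. If subjects switch because the new product leaks, the poorest outcomes leave the analysis and the reported change is better than the change among all enrolled.

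At stake is what the report may conclude on QoL and leakage. The usability outcome is primary and descriptive, and is not touched.

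**Working it through.** **1. The plan's own figure.** Section 6 gives at least 40 subjects in each of 4 countries: 4 × 40 = 160, the stated minimum. It rests on feasibility. No power, SD or effect size is given, so there is no power figure to reproduce.

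**2. The passages side by side.** The QoL wording in 3.2 and 4 asks about an effect. The analysis wording in 7 and 8.2 speaks of change in domain scores before and after transition. The analysis matches the second wording and cannot answer the first. On data handling, section 4 requests the second questionnaire from those who stop the recommended product. Sections 5.3 and 7 discard the data of those who move to another product. Someone who stops the recommended product will usually be wearing another, so the two groups largely overlap. The data are requested but have no stated use.

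**3. Removal of switchers (illustration; all inputs assumed).** Let the change D be standard normal with no true effect. Let a removal signal have correlation ρ with a worse change, and remove the top fraction f. With z the upper-f normal quantile and φ the normal density:

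- shift toward improvement = ρ·φ(z)/(1 − f)
- 95% CI half-width = t(0.975, n − 1)·SD(D among retained)/√n

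With 160 enrolled in the analysed group:

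| f | n analysed | φ(z) | shift, ρ = 0 | shift, ρ = 0.3 | shift, ρ = 0.5 | half-width, ρ = 0 to 0.5 |
|---|---|---|---|---|---|---|
| 5% | 152 | 0.103 | 0 | 0.033 | 0.054 | 0.160 to 0.156 |
| 10% | 144 | 0.175 | 0 | 0.058 | 0.097 | 0.165 to 0.159 |
| 20% | 128 | 0.280 | 0 | 0.105 | 0.175 | 0.175 to 0.166 |

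Example: f = 10%, ρ = 0.3 gives 0.3 × 0.1755/0.9 = 0.058 SD against a half-width of 0.163 SD. With 120 enrolled in the analysed group (an assumption, since the number of NPDs is not given) the shifts are the same and the half-widths run from 0.181 to 0.203. The shift exceeds the half-width in one cell only: 20% removed, ρ = 0.5, 160 enrolled (0.175 against 0.166).

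**4. Regression to the mean (illustration; all inputs assumed).** Let the weekly leakage count have unit variance and week-to-week correlation r, with no true effect.

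- Entry on the stable level: shift 0.
- Entry as the worst half on a 13-week average that includes the baseline week: shift = [(1 − r)/13]/√[r + (1 − r)/13] × 0.798. This gives 0.042 (r = 0.5), 0.022 (r = 0.7) and 0.006 (r = 0.9) SD. The half-width is t·√[2(1 − r)]/√n: 0.156, 0.121 and 0.070 at n = 160; 0.181, 0.140 and 0.081 at n = 120. The ratio is 8% to 27%.
- Entry on the baseline score itself, at least c SD worse than average: shift = (1 − r)·φ(c)/[1 − Φ(c)]. For r from 0.9 to 0.5 and c from 0 to 1 this gives 0.08 to 0.76 SD.

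The result runs from 0 to 0.76 SD depending only on the assumed entry rule. The documents do not state that rule in a form that would select one of these.

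**5. The remaining contributors** (re-evaluation, support calls, unblinded recall, body profile change) cannot be sized from the documents.

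**The case against.** **The design is disclosed and the wording hedged.** Section 4 states one arm without blinding, and section 9 states no control. Both QoL phrases follow the words to explore, and the analysis sections already speak of change. This stands in part: the design can stay and the rewording is small. But a hedge does not make an uncontrolled change attributable, and no sentence in the plan tells the reader that it is not.

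**The size is assumed throughout.** This stands. Every input in steps 3 and 4 is assumed and both ranges include zero. A reader might infer that a significant result would be mostly regression to the mean. The documents do not support that. Section 4 refers to continuing product problems, which fits entry on a stable level, where the shift is nil. Nor can the argument be confined strictly to veterans: NPDs have no leakage criterion in 5.2, but the section 4 text on identifying patients does not separate the groups.

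**The leakage objective claims no effect.** This stands. The wording problem concerns QoL; the limit on interpretation applies to both tests.

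**The arrival product may be collected elsewhere.** This stands. Appendix D as shown begins at part 2, and no form as shown holds age, time since stoma debut or reason for discontinuation, so the visible forms may not be the full record. A reader might infer that the arrival product is not recorded, or that the 8.2 analysis of product solution and leakage cannot run. Neither follows: the first is open, and the second can use the chosen product.

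**Conclusion.** The point holds in limited form. A significant paired t-test on OLI or leakage would show change from before to after and nothing about cause, so it would not support the effect wording on QoL in 3.2 and 4. Removing switchers may tilt that change toward improvement; the plan requests data that would let this be examined but gives them no use. The shift is 0 if switching is unrelated to outcome. It reaches 0.175 SD of the change at 20% removed with correlation 0.5, against half-widths of about 0.16 to 0.20 SD, and these inputs are assumptions and not findings about this trial. Only secondary outcomes are affected. The documents do not support reading this as a reason to add a control group, or as evidence that the results will be biased.

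**What to change.** 1. **Main change.** Keep the planned paired analysis and report how many subjects were removed for changing product. Add a supportive paired analysis (mean change with 95% CI) of all enrolled subjects with both questionnaires, including those who changed or stopped the recommended product, separately for veterans and NPDs. Reconcile sections 4, 5.3 and 7 so that these data are kept for it. It will still miss those who do not return the second questionnaire.

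2. **Wording.** In 3.2, state the QoL objective as: *to explore the change in leakage-associated QoL (OLI score) from before to after body profile assessment and product change*. Reword the whole section 4 clause in the same way, including can reduce. Add to section 9 that the comparison does not separate the tool or product change from the nurse re-evaluation and support calls, unblinded self-report, change in peristomal body profile over time (especially NPDs), removal of product changers, or regression to the mean (mainly veterans).

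3. **Arrival product.** If it is not already collected on a page not shown, record plate, system and bag in use on arrival at the existing visit, and report the share whose type changed. Section 1 names the tool's impact on product selection as a question, and this share describes it. Use a separate record: a row added to Appendix A would alter the tool whose usability is the primary outcome.

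**Cost.** A few more fields, one extra analysis and a more modest claim. No extra visit or subjects are needed.
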